Exclusion criteria: (a) Diabetes mellitus or other diseases potentially associated with autonomic dysfunction [17]; (b) Treatment with antihypertensive drugs or with alpha-adrenergic antagonists; (c) Cognitive impairment, defined as a score $<$ 24 at the Montreal Cognitive Assessment (MoCA) [18]; (d) Any atypical signs lowering the diagnostic certainty for PD; (e) Lack of postural reflex defined as a score $>$ 2 at the MDS-UPDRS [13] item 3.12 [recover at the pull test]; (f) Severe levodopa induced dyskinesia, defined as a MDS-UPDRS item 4.2 $>$ 2 [functional impact of dyskinesia].

Pharmacological Therapies

Changes in medications or dosages that may affect blood pressure, other than Droxidopa, will not be allowed for the entire duration of the study (6 weeks).

Study Assessment/Procedures

Screening Visit: The PI or a member of the study team will explain the purpose, procedure, potential risks and benefits of this study, obtain the informed consent, and screen patients for Inclusion/Exclusion criteria.

Visit 1: This evaluation will be performed at least 1 hour after the first dose of dopaminergic medications, when patients are expected to be at their most optimized level of motor function. BP assessment, as per autonomic laboratory protocol, will be performed with a beat-to-beat BP monitor (Caretaker 4, Caretaker, VA, USA) and confirmed by an automated sphygmomanometer (HEM-7200 Omron Healthcare, Japan) placed at heart level on the left arm, evaluating patients in the following conditions: a) sitting in a chair

after at least 10 minutes of rest; b) after a minimum of 10 minutes of supine rest; and c) after 1 and 3 minutes of standing. These measurements will serve to (1) confirm the diagnosis of OH, and (2) evaluate for the presence of SH, defined as systolic BP \geq 150 mmHg or diastolic BP \geq 90 mmHg in the supine position [19]. Arm-cuff BP measurements will be performed with the upper arm positioned at the heart level with the feet flat on the floor. Patients will also receive training to self-monitoring BP with automated arm-cuff sphygmomanometer, which will be provided at Visit 1, and will serve to monitor BP during Droxidopa titration plan.

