Clinical Assessments: Motor severity as per the MDS-Unified Parkinson's Disease Rating Scale (MDS UPDRS) [20]; OH symptoms severity as per the full OHQ (OHSA and OHDAS) scale [7]; quality of life as per the PD questionnaire (PDQ-39) [11]; Cognitive assessment as per the Cambridge automated neuropsychological test battery (CANTAB) [12] and CERAD-NAB [13].

Clinical Diary: Patient will be instructed to score the severity of the OH-related episodes of postural instability and the number of episodes of postural instability a day before starting titration with droxidopa, 1 day after V2 and 1 day after V3; using a self-assessed clinical diary based on the OHDAS (a section of the OHQ assessing the impact of OH symptoms on standing and walking).

Gait Assessments (average of two measurements): In order to evaluate variables of interest (stride length, single leg stance time, dynamic stability index, and gait velocity), patients will be assessed walking on the 20 feet-Protokinetics Zeno Walkway. Patients will be instructed to "walk from the mark (red tape) before the mat to the mark after the mat, turn around and walk back". After a preliminary review for acquisition errors, the data will downloaded into a Matlab-based software platform prepared ad-hoc for this study (Matlab, Mathworks, CA, USA) by the Department of Bioengineering of the University of Cincinnati ([name]).

Postural Assessments (average of two measurements): In order to evaluate variables of interest (postural sway on the X and Y-axis, as measured by the center of mass estimated X and Y range), patients will be asked to perform a modified Clinical Test of Sensory Interaction on Balance. Patients will stand on the mat for 30 seconds under the 2 following conditions: eyes open/rest and eyes closed/rest, with their feet 1"-2" apart and arms at their side. For the eyes open condition, he/she will be asked to focus on a point in front of him/her at eye level to control for visual distractions. Data will be collected and stored into the software platform described above.

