WMS Assessment: Patients will be provided an Apple Watch® with dedicated app (e.g., the Activity app®), able to measure number of hours of standing per day, and total calories and active calories per day. The Apple Watch® will be connected with an iPhone and will be given to each subject together with dedicated instructions to fill out the OH-related diary. More in details, patients will be instructed to charge the Apple Watch® and the iPhone® every night before going to bed, and to wear the watch the day after when they wake up. Total number of hours in which the patients will wear the watch will be counted at the end of the study, based on the data provided by the Apple Watch®. Data collected by the Apple Watch® will be downloaded after the end of the study and will provide information related to number of steps per day, number of hours of standing per day, and total calories and active calories per day.

Droxidopa Titration Plan

Droxidopa will be started after 2 days of baseline data collection at the dosage of 100 mg 3 times a day (TID). Dose-optimization will be titrated over a 2-week period in 100- mg TID increments every 2 days until at least one of the following criteria is met:

- Self-rating score of 0 at the item 1 of the OHQ, plus an increase in standing systolic BP ≥ 10 mm Hg, compared with the baseline value, as measured 3 minutes post-standing (and 3 hours after a Droxidopa dose).
- Reaching the maximum permitted dosage of 600 mg TID.
- Sustained BP > 180 mmHg systolic or > 110 mmHg diastolic while standing, sitting, or supine.

Visit 2: Patients will receive a complete BP assessment following the same procedure detailed in Visit 1 (see above), and a standard neurological examination. Adverse events and side effects associated with Droxidopa treatment will also be addressed, adjusting the dosage of Droxidopa if needed. Technical issues related to the use of Apple Watch® will also be discussed, if present.

Visit 3: This evaluation will be performed in the morning, at 8:00 AM before breakfast and at least 1 hour after the first dose of dopaminergic medications, 4 weeks after Visit 2. Patients will undergo a complete clinical, gait, postural and BP assessment, as per the protocol described in Visit 1.

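### No blood pressure reading or action limit is planned for the 4 weeks between Visit 2, where the Droxidopa dose may be adjusted, and Visit 3

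*Combined protocol and SAP*

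**What the plan says.** All references are to the combined protocol and SAP.

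- **Home cuff** (Study Assessment/Procedures, Visit 1). "Patients will also receive training to self-monitoring BP with automated arm-cuff sphygmomanometer". The same sentence then gives the purpose of the device: "which will be provided at Visit 1, and will serve to monitor BP during Droxidopa titration plan". No frequency of home readings is stated.
- **Titration** (Droxidopa Titration Plan). The dose is "titrated over a 2-week period in 100- mg TID increments every 2 days until at least one of the following criteria is met". One criterion combines symptom relief with a rise in standing systolic pressure. The other two are "Reaching the maximum permitted dosage of 600 mg TID" and "Sustained BP > 180 mmHg systolic or > 110 mmHg diastolic while standing, sitting, or supine".
- **Visit 2.** The full pressure assessment of Visit 1 is repeated and adverse events are reviewed, "adjusting the dosage of Droxidopa if needed". No pressure threshold is attached to that adjustment.
- **Visit 3.** It takes place "4 weeks after Visit 2. Patients will undergo a complete clinical, gait, postural and BP assessment, as per the protocol described in Visit 1".
- **Other home items.** The diary is completed "a day before starting titration with droxidopa, 1 day after V2 and 1 day after V3" and scores postural instability. The watch records steps, standing hours and calories, and its data are downloaded after the study ends.

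**The concern.** The plan treats high pressure as a hazard of this drug. It looks for supine hypertension at Visit 1, it stops dose increases above 180/110, and Risks and Benefits rates the study as more than minimal risk. The written monitoring then stops where the longest period on treatment begins.

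Three features add to this:

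- Supine hypertension is evaluated but is not among the exclusion criteria.
- A patient whose titration ended because pressure passed 180/110 is told only that increases stop. The text does not call for a reduction, although Visit 2 may make one.
- Pharmacological Therapies bars changes for 6 weeks to any other medicine that affects blood pressure. The Droxidopa dose is therefore the one drug lever the protocol leaves open, and no maintenance trigger is given for using it.

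At stake is high pressure without symptoms that begins after Visit 2. If the plan is followed as written, the study might not see it until Visit 3.

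**Working it through.** The plan gives no figure to reproduce, so the check sets the schedule side by side and adds simple arithmetic.

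| Period | Planned pressure reading | Pressure limit and stated action |
|---|---|---|
| Visit 1 | Full: sitting, supine, standing at 1 and 3 minutes | Supine hypertension (150/90 or above) noted; no action attached |
| Titration, 2 weeks | Home cuff, frequency not stated | Sustained >180 or >110 ends dose increases |
| Visit 2 | Full, as Visit 1 | Dose adjusted if needed; no threshold |
| Visit 2 to Visit 3, 4 weeks | None stated | None stated |
| Visit 3 | Full, as Visit 1 | None stated |

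**Does any other text fill the empty row?** The diary entry 1 day after Visit 2 does not record pressure, and neither does the watch. Risks and Benefits says that titration and side effects are explained before the drug is started, but sets no monitoring during maintenance. Nothing in the supplied text fills the row.

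**Length of the gap.** Visit 3 is dated from Visit 2, so 4 × 7 = 28 days. This does not depend on when Visit 2 falls. Experimental Design and Patient Population gives 2 + 4 = 6 weeks of treatment, so the gap is 4/6 = 67% of treatment time.

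**Dose held over the gap.** At most 600 × 3 = 1,800 mg/day. From 100 to 600 mg three times daily is 5 steps, and 5 × 2 days = day 10. If Visit 2 falls at day 14, the end of titration (inferred from the 2 + 4 week schedule), a patient who climbs without pause has held the maximum for 14 − 10 = 4 days when pressure is checked there. A patient whose dose is changed at Visit 2 has had no planned check on the new dose until Visit 3.

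**Effect of weekly home readings.** Readings on days 7, 14 and 21 after Visit 2 cut the longest interval from 28 to 7 days.

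- Weekly sessions: 3 per patient, 3 × 12 = 36 in total.
- With one extra session per dose change and *d* changes across all patients: 36 + *d*. If each of the 12 patients has exactly one change, 36 + 12 = 48.
- Time, if the Visit 1 rest periods are copied: 10 + 10 + 3 = 23 minutes per session. This is 3 × 23 = 69 minutes per patient, or 4 × 23 = 92 with one dose change. Shorter rests would take less.

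**The case against.** The strongest reply is that the gap is shown only for the text supplied. The protocol attaches a patient brochure on Droxidopa and a separate consent document, neither of which was available for review, and these are natural places for advice on home readings and when to call. The drug is prescribed by the treating physician, whose own follow-up is not described. Droxidopa is exempt from the ban on medication changes, so its dose can be cut at any time. Nothing withdraws the cuff after titration. All of this stands. It limits the point to what the study plan states, but does not remove it: the protocol sets the titration scheme itself and restricts other pressure-related treatment, so it should also state the monitoring.

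A second reply is that pressure is watched while the dose is moving and is checked in full at Visit 2, so most patients then hold a dose already checked. That is fair for patients whose dose is unchanged at Visit 2, if Visit 2 comes at the end of titration. It does not cover those whose dose is changed there, or a rise that develops later.

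A third reply is that no text supports weekly readings over another interval. That is correct; the weekly interval is a proposal.

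Stronger readings are tempting, and the documents do not support them:

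- *Patients go unmonitored for 4 weeks.* The text shows only that the study plans no reading.
- *Home readings stop after titration.* The plan states a purpose for the cuff and does not say that use must end.
- *The maximum dose is six times the starting dose (1,800 against 300 mg/day), so the risk is several-fold higher.* A dose ratio says nothing about the frequency of hypertension.

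**Conclusion.** The point holds as a patient-safety gap in the study plan, and it should be closed. Between Visit 2 and Visit 3 the supplied text has no pressure reading and no pressure action limit for 28 days, 4 of the 6 treatment weeks, at up to 600 mg three times daily. The 180/110 limit exists but serves only to end dose increases.

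The size of the risk cannot be given, because the documents contain no event rate; the 28 days describe the schedule. No endpoint, analysis or error rate is affected. The conclusion assumes that the brochure and consent form do not already set home readings and a reporting limit for maintenance. If they do, what remains is a need to align the protocol with them.

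**What to change.** 1. In the Visit 1 text, extend the stated purpose of the home cuff so that it covers titration and continues until Visit 3.
2. After the Visit 2 text, add that patients measure pressure at home supine, sitting and standing at a set interval, for example weekly (days 7, 14 and 21 after Visit 2), and again 2 days after any Droxidopa dose change. The 2 days match the plan's own titration step.
3. Add that sustained readings above 180 systolic or 110 diastolic are reported to the study physician, who decides on dose reduction with the treating neurologist.
4. Record any dose change before Visit 3 with its date.
5. If the brochure or consent form already says this, bring the protocol into line with it.

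**Cost.** Cuff and training are already provided. New costs are a short protocol change, matching patient instructions, a reporting route, occasional calls and some physician time. Weekly readings add 36 home sessions, plus one per dose change. There is no fixed maximum: 48 is the total if each patient has exactly one change, and an interim reduction adds another session.

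**Downside.** An interim dose cut changes the dose at which gait is measured again at Visit 3, which is why step 4 is needed. The protocol already permits Droxidopa changes, so no rule has to be relaxed.

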The main objective of this study is to evaluate the feasibility of using TOMs in the assessment of OH-associated postural stability, both “in-clinic” and “at-home”. Twelve consecutive PD patients with OH about to start pharmacological treatment with vasopressor agents prescribed by their neurologist will undergo gait and postural assessments (Protokinetic Zeno Walkway) before and after treatment with vasopressor agents (Droxidopa). Patients will also use wearable motion sensors (WMS) (Apple Watch® - Apple, Cupertino, CA, USA) for monitoring their normal activities of daily living. Gait analysis will measure the improvement in stride length and velocity, double-support time (percentage of time spent with both feet in contact with the ground), and postural sway on the anteroposterior and lateral axis, both at baseline (before treatment with Droxidopa) and after 6 weeks of therapy (2 weeks of dose-titration plus 4 weeks of maintenance therapy). Data collected by TOMs (a) before and (b) after treatment with Droxidopa, will be correlated with changes in conventional scales of postural stability (Tinetti balance scale) [10], OH questionnaire (OHQ) [7], quality of life measures (39-Item Parkinson's disease questionnaire, PDQ-39)[11], and cognitive functions (Cambridge neuropsychological test automated battery – CANTAB - Connect Research, Cambridge Cognition Ltd., UK - and CERAD-NAB).[12, 13]

Our **central hypothesis** is that TOMs will result in higher detection power and lower variability than conventional clinical assessments, also minimizing interferences due to the placebo effect. If confirmed, these findings will improve the treatment in PD by using TOMs, instead of standard subjective outcome measures.

AIMS OF THE STUDY

The two aims of this study are:

Aim #1: To evaluate the feasibility and effect-size of using gait and postural tests to quantify OH related postural stability during in-clinic evaluations:

PD patients with newly diagnosed OH (n = 12) will be assessed at baseline and after 1 month of anti-OH treatment with the following tests:

Clinical tests: OHQ score (OH Symptom Assessment, OHSA and Orthostatic Hypotension Daily Activities Scale, OHDAS), Tinetti score, PDQ-39 score.

Gait analysis: stride length, single leg stance time, dynamic stability index, and gait velocity

Postural analysis: postural sway on the X and Y-axis.

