Hypothesis: Gait analysis and Postural analysis will accurately capture changes in gait and postural stability associated with OH treatment, with higher sensitivity and lower variability than standard clinical tests.

Aim #2 To evaluate the feasibility and calculate the effect size of using WMS to quantify OH related postural instability during at-home activities of daily living

Gait and postural stability will be evaluated in the home environment by means of the following outcome measures:

Clinical assessment: Self-assessed clinical diary (OHDAS-based score) evaluating the subjective sensation of postural instability and number of episodes of postural instability.

WMS assessment: WMS (Apple Watch®) evaluating functional parameters, namely a) number of steps per day; b) number of hours of standing per day; c) total calories and active calories per day.

Hypothesis: TOMs will provide an accurate measure of functional parameters in the home setting, thus allowing an indirect measure of the patients' quality of life, with higher sensitivity and lower variability than self-reported clinical diaries.

INVESTIGATOR EXPERIENCE: Please see attached Bio sketch.

CLINICAL EVALUATIONS

Screening Assessment (Day 0)

12 consecutively consenting PD patients with OH about to start pharmacological treatment with a vasopressor agent (Droxidopa), as prescribed by their treating physician from the Gardner Family Center for Parkinson's Disease and Movement Disorders, will be screened for the following inclusion/exclusion criteria:

Inclusion criteria: (a) Diagnosis of idiopathic PD, meeting UK Brain Bank criteria [15] for at least 3 years; (b) Hoehn and Yahr (H&Y) stage I-III; (c) Age between 30 and 80 years old (both inclusive); (d) Stable dosage of dopaminergic medications for at least 4 weeks; (e) OH, defined as a fall in systolic BP \geq 20 mmHg or diastolic BP \geq 10 mmHg within 3 minutes of standing [16]; (f) Willingness and ability to comply with scheduled visits.

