Data will be described with appropriate summary measures (mean and SD, or median and interquartile range) at Visit 1 (before Droxidopa treatment) and Visit 3 (after 4 weeks of Droxidopa maintenance therapy). Changes in the main clinical (PDQ-39, Tinetti, OHQ and related subscales), gait (stride length, single leg stance time, dynamic stability index, and gait velocity) and postural (postural sway on the X and Y axis) outcomes will be compared between Visit 1 and Visit 3 using the paired t-test/ non parametric Wilcoxon signed rank test depending on the distribution of change outcome. Effect size (mean or median change and percent change) will be reported along with 95% confidence interval (CI). In addition, data collected with TOMs before and after treatment with Droxidopa will be correlated with changes in the PDQ-39, OHQ, CANTAB and CERAD-NAB by means of the Pearson correlation/Spearman rank correlation analysis.

Hypothesis: Gait analysis and Postural analysis will accurately capture changes in gait and postural stability associated with OH treatment, with higher sensitivity and lower variability than standard clinical tests.

Aim #2 To evaluate the feasibility and calculate the effect size of using WMS to quantify OH related functional parameters during at-home activities of daily living

Postural data collected from WMS (Apple Watch®) and evaluating: (1) Number of steps per day; (2) number of hours of standing per day; and (3) total calories and active calories per day, will be analyzed and compared with episodes of subjective (OHDAS-based diary) postural instability recorded during the follow-up period using a paired t-test/Wilcoxon signed rank test. In addition, we would also evaluate the changes from pre-baseline to post baseline of subjective measure of postural stability and correlate with objective measures of postural stability using Pearson correlation/Spearman rank correlation analysis. Statistical analyses will be carried out using SAS 9.3.

Hypothesis: WMS will provide an accurate measure of functional parameters in the home setting, thus allowing an indirect measure of the patients' quality of life, with higher sensitivity and lower variability than self-reported clinical diaries.

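### The only untreated watch period described is 2 days, so those days dominate the day-to-day error of any before-after watch change; earlier hand-over of the watch would be a cheap improvement.

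*Combined protocol and SAP*

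**What the plan says.** Under Droxidopa Titration Plan: "Droxidopa will be started after 2 days of baseline data collection". Under Experimental Design and Patient Population, the second assessment comes "after 6 weeks of therapy (2 weeks of dose-titration plus 4 weeks of maintenance therapy"; Visit 3 is set "4 weeks after Visit 2", which gives 28 maintenance days.

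The WMS Assessment paragraph lists the watch measures as "number of steps per day, number of hours of standing per day, and total calories and active calories per day". It stands among the Visit 1 procedures, so hand-over at Visit 1 is the natural reading, although it is not stated outright. Hours of wear are to be counted, but no minimum for a valid day is given.

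Aim #2 is to "calculate the effect size of using WMS to quantify OH related postural instability during at-home activities of daily living"; the Data Analysis section words it as to "calculate the effect size of using WMS to quantify OH related functional parameters". The paired test written there sets watch data against diary episodes of "postural instability recorded during the follow-up period using a paired t-test/Wilcoxon signed rank test". Experimental Design also says that TOM data from before and after treatment will be correlated with changes in the clinical scales. A before-after watch contrast is therefore implied, but the plan does not define which watch days count as before and which as after.

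Consent comes earlier: at the Screening Visit the team will "obtain the informed consent, and screen patients for Inclusion/Exclusion criteria".

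**The concern.** Activity varies from day to day, and 2 consecutive days cannot cover a week. Any watch effect size must use those 2 days as its untreated reference, however many treated days follow. Correcting the Aim 2 test alone would not change this.

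Three outputs are affected: the precision of the effect size meant to inform a larger proposal; the correlations, which use each patient's own change; and the hypothesis that the watch is less variable than the diary, because part of the watch's variability would reflect how few days were sampled and not how the device performs.

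**Working it through.** **The plan's own figure.** The only sample-size calculation is for stride length (Aim 1). A paired t-test with 12 patients, a 30% change and an SD of 31.3% has 85.5% power two-sided; at the 10% threshold it has 17.3%. That is a separate Aim 1 matter. No figure is given for the watch, so there is nothing to reproduce for this point.

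**Inputs.** From the protocol: b = 2 baseline days, m = 28 maintenance days, n = 12. Assumed: within-patient day-to-day CV of 25% to 45%, independent days, weekends 20% less active than weekdays. The 10% yardstick below is borrowed from the stride-length threshold.

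**Share of day-to-day variance from the baseline.** (1/b)/(1/b + 1/m) = 0.5/(0.5 + 0.0357) = 93%.

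**Standard error of the group mean change, day noise only.** SE = CV × √(1/b + 1/m)/√12. The root is 0.732 for b = 2 and 0.423 for b = 7.

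| CV | SE, 2 days | SE, 7 days |
|---|---|---|
| 25% | 5.3% | 3.0% |
| 35% | 7.4% | 4.3% |
| 45% | 9.5% | 5.5% |

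The reduction is 1 − 0.423/0.732 = 42% at any CV. With t(11) = 2.201, the 95% half-width at 2 days reaches 10% at a CV of 21.5%; one SE reaches 10% only at 47.3%.

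**One patient's change.** Noise SD = 0.732 × CV, which reaches 10% at a CV of 10/0.732 = 13.7%.

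**With true differences in response between patients (SD s, assumed).** SD of change = √(s² + CV²(1/b + 1/m)).
- CV 25%, s = 20%: 27.1% with 2 days and 22.6% with 7, a 17% cut.
- CV 45%, s = 10%: 34.4% and 21.5%, a 38% cut.
- CV 35%, s = 15%: 29.7% and 21.1%. The variance ratio (29.7/21.1)² is about 2, so a later study sized on the first SD would need about twice the patients.

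**Weekday mix.** With weekdays at 1.0 and weekends at 0.8, the weekly mean is (5 + 2 × 0.8)/7 = 0.943. Suppose Visit 1 falls evenly on Monday to Friday and the next 2 days are baseline. The five baselines are 1.0, 1.0, 1.0, 0.9 and 0.8: mean 0.940, SD 0.08. The group shift is about 0.3 points; the spread between patients is about 8 points. If every baseline is weekday-only, the spurious change is 0.943 − 1 = −5.7%.

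**Cost of matching on the same weekdays.** Two baseline days match 2 × 4 = 8 maintenance days: √(1/2 + 1/8) = 0.791, and 0.791/0.732 is an SE 8% larger. Dropping the first wear day as well leaves 1 against 4: √(1 + 1/4) = 1.118, an SE 53% larger.

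**The case against.** This is a 12-patient feasibility pilot in patients about to start a prescribed drug. A short run-in is a defensible compromise, and a wide confidence interval would disclose the imprecision. The more basic gap is that the plan never defines the before and after windows for the watch. Both points stand, and they limit this to an improvement. They do not remove it: any sensible window definition still has only 2 untreated days, and a treated window shorter than 28 days would add noise.

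A reader might infer more than the documents support:

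- *Noise will swamp the effect.* No target change or day-to-day SD is stated for any watch measure, and 10% is a stride-length figure. At a CV of 20% the group half-width is 9.3%, still below it.
- *Weekday error runs one way and survives averaging.* With visits spread evenly over the working week it nearly cancels. A common direction needs baselines concentrated on weekdays, for example through early-week visits or counting the visit day itself. The protocol states neither.
- *The first day is partial, or novelty distorts it.* Patients are told to put the watch on when they wake the day after charging it, which points to full days. Nothing in the documents bears on novelty.
- *The baseline sets the precision almost entirely.* That is true of day-to-day noise only, not of differences in response between patients.

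**Conclusion.** The point holds as one of precision. Two untreated days supply about 93% of the day-to-day variance of a before-after watch change; that share follows from the protocol's own day counts if days are independent with equal variance. Positive correlation between adjacent days would make a 2-day mean less precise still.

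The size in percent rests on an assumed CV. Seven baseline days would cut the day-noise SE by 42%, and the full SE by 17% to 38% under the response SDs assumed above. Patient-level changes, and so the correlations, suffer most: their noise SD passes 10% at a CV of about 14%. Systematic weekday bias in the group mean is conditional on clustered baselines and on the assumed 20% weekend drop, with a ceiling of about 6%. The documents do not show that noise or weekday mix will exceed the watch effect.

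**What to change.** 1. Hand out the watch at the Screening Visit, after consent. Define baseline as all untreated wear days from then through the existing 2 days. When Droxidopa starts does not change.
2. Write the contrast into Data Analysis, Aim #2: untreated days against all maintenance days, leaving out titration, in a day-level model with the patient as the unit of inference and a weekday-versus-weekend term. Four full maintenance weeks give 20 weekdays and 8 weekend days per patient from which to estimate that term.
3. Do not match on the same weekdays by discarding maintenance days, and do not drop the first wear day by rule. Both widen the SE, as shown above.

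The cost is small: the study already supplies the device, and the analysis change is a short paragraph. Watches issued to screen failures must be recovered. Item 1 helps only where screening and Visit 1 fall on different days; the protocol labels screening Day 0 and states no interval. If they coincide, no baseline days are gained, and item 2 still deals with weekday mix but leaves the 2-day imprecision, which should then be reported with the effect size.

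### No upper blood pressure limit is stated for starting Droxidopa, so a patient already persistently above the plan's own 180/110 level could be given the first 100 mg TID

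*Combined protocol and SAP*

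**What the plan says.** All references are to the combined protocol and SAP.

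- **Entry (Screening Assessment, Day 0).** The only BP inclusion criterion is "e) OH, defined as a fall in systolic BP" of at least 20 mmHg, or diastolic of at least 10 mmHg, within 3 minutes of standing. The only exclusion that concerns BP is "b) Treatment with antihypertensive drugs or with alpha-adrenergic antagonists".
- **Visit 1 (Study Assessment/Procedures).** Sitting, supine and standing BP are taken with a beat-to-beat monitor and an arm cuff. The readings confirm OH and "evaluate for the presence of SH, defined as systolic BP" of at least 150 mmHg, or diastolic of at least 90 mmHg, when supine. No action is attached to an SH finding.
- **Start (Droxidopa Titration Plan).** "Droxidopa will be started after 2 days of baseline data collection at the dosage of 100 mg 3 times a day (TID").
- **Escalation (same section).** The dose then rises in 100 mg "TID increments every 2 days until at least one of the following criteria is met". One criterion is "Sustained BP > 180 mmHg systolic or > 110 mmHg diastolic while standing, sitting, or supine"; another is "Reaching the maximum permitted dosage of 600 mg TID".
- **Other drugs (Pharmacological Therapies).** For the 6 weeks, no other medication that may affect BP may be changed.

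**The concern.** The plan names a BP level at which it will not add a further 100 mg TID of a vasopressor. Going from no drug to 100 mg TID is a step of the same size, yet the text does not apply that level to it, although supine, sitting and standing BP are measured beforehand. What is at stake is patient safety. A patient with very high untreated BP, most plausibly when supine, could begin a pressor drug under a protocol that has already recorded the reading. Because other BP-related drug changes are barred, Droxidopa itself is the only drug adjustment the protocol allows, so the decision to start carries more weight.

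**Working it through.** There is no planned figure to reproduce. The check applies the written rules to example patients and does the simple dose and timing arithmetic.

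**1. Is there a ceiling at entry?** Inclusion (a) to (f) gives 6 criteria and exclusion (a) to (f) gives 6, so 12 in total. The number that set an absolute BP level is 0. Inclusion (e) concerns a difference between positions. Exclusion (b) concerns treatment, so untreated high BP is not caught.

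**2. Can one patient meet the OH criterion and already exceed 180/110?** The rules are:

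- OH: supine minus standing is at least 20 systolic or at least 10 diastolic.
- SH: supine is at least 150 systolic or at least 90 diastolic.
- Limit: above 180 systolic or above 110 diastolic in any position.

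The BP values below are assumed for illustration.

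| Supine | Standing | Fall | OH | SH | Above 180/110 |
|---|---|---|---|---|---|
| 190/100 | 165/92 | 25/8 | yes | yes | yes |
| 185/112 | 160/100 | 25/12 | yes | yes | yes |
| 210/115 | 185/112 | 25/3 | yes | yes | yes |
| 140/80 | 115/70 | 25/10 | yes | no | no |

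The first three patients satisfy inclusion (e). If they take no antihypertensive or alpha-antagonist, no exclusion removes them on BP grounds.

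**3. What does the text then do with them?** The start sentence applies to each, giving 100 mg TID. If the high BP persists, the 180/110 criterion prevents the step to 200 mg TID. It does not require the drug to be withdrawn.

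**4. How much drug is involved?** The held dose is 100 × 3 = 300 mg/day. The maximum is 600 × 3 = 1,800 mg/day. The ratio is 300 / 1,800 = 16.7%, one sixth. The gap therefore concerns starting and staying on the lowest dose.

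**5. When is the next clinic reading?** Therapy lasts 6 weeks and Visit 3 falls 4 weeks after Visit 2. Visit 2 is therefore about 6 − 4 = 2 weeks, or 14 days, after the first dose. Home cuff readings come sooner, and nothing bars acting on them.

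**The case against.** Four arguments on the other side have weight.

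**The first dose may belong to titration.** The start sentence sits under the titration heading. The Clinical Diary paragraph places an entry on the day before titration begins, and the 6 weeks of therapy are counted as 2 of titration plus 4 of maintenance. On that reading, a patient already above 180/110 meets an end criterion at time zero and would not be started. The reading is reasonable, but the criterion is worded to govern increments, so the text leaves room for either interpretation. The plan also does not define what counts as sustained.

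**The treating physician has already decided to prescribe.** That is a real filter, and exclusion (b) removes treated hypertensives. However, the prescribing decision precedes the Visit 1 measurements, and the text does not say that these reach the prescriber before dosing. A patient excluded from the study could still receive the drug from that physician, so the fix informs that decision without controlling it.

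**A limit may be written elsewhere.** Visit 1 refers to "BP assessment, as per autonomic laboratory protocol", and the patient brochure and consent form are separate documents. None could be checked. If one holds a start limit, a cross-reference closes the point.

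**180/110 is an on-treatment level.** Using it as a start limit is an analogy. It is the natural default because the plan already uses it for a dose step of equal size, but the study team could justify another level.

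A reader might go further and infer that no BP condition applies at all, that the plan contradicts itself, that such a patient would be escalated, or that the effect sizes are compromised. The documents support none of these. The OH fall is a BP condition for entry. Silence about the start is a gap and not a contradiction. The 180/110 rule stops escalation while the high BP is sustained. Nothing shown here bears on the effect-size estimates.

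**Conclusion.** The point holds in a limited form: the supplied text states no upper BP limit for starting Droxidopa, and its literal wording allows a first dose in a patient persistently above the level at which the plan stops adding drug.

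It is a modest safety gap. The documents give no frequency of baseline BP above 180/110, so the number affected is unknown and may be 0 of 12, and no risk can be estimated. Exposure is limited to 300 mg/day for as long as BP stays above the limit.

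The conclusion assumes that the 180/110 criterion governs increments only, as worded, and that no attachment contains a start limit. Prescriber judgement may prevent the case in practice. A stated limit is still worthwhile, because the readings exist before dosing and the protocol itself fixes the timing and size of the first dose.

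**What to change.** Make three short additions.

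1. **Eligibility criteria:** exclude a patient whose Visit 1 BP is above 180 mmHg systolic or above 110 mmHg diastolic when standing, sitting or supine, if a repeat measurement in the same position at the same visit confirms it. Use the beat-to-beat monitor and the cuff already in place.
2. **Droxidopa Titration Plan:** state that Droxidopa is not started under the protocol in that case. If an attachment already sets a start limit, cite it here.
3. **Visit 1:** report any reading above 180/110, and any SH (at least 150 systolic or at least 90 diastolic, supine), to the treating physician before the first dose. SH alone does not exclude. Treatment outside the study remains that physician's decision.

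Confirming at the same visit avoids excluding a patient on one stray reading and needs no new pre-dose contact with the patient. It does not show persistence across days, which is an acceptable trade-off.

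The cost is a few repeat readings, a note to the physician and an occasional screen failure. Recruitment of 12 patients runs over months 2 to 10, which is 8 months. At an even rate, replacing one patient takes 8 / 12 = 0.67 month.
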